6.1.2 Calculation or derivation of pharmacodynamic variables

Blood samples (10 mL) will be collected for assessment of pharmacodynamic (lipid) parameters on the mornings of Days –1 and 18.

Pharmacodynamic variables will include the following:

tChol	total cholesterol
LDL-C	low-density lipoprotein cholesterol
HDL-C	high density lipoprotein cholesterol
TG	triglycerides

6.1.3 Population analyses – Not applicable

6.2 Safety evaluation

Safety and tolerability will be assessed by the incidence and severity of AEs, clinical laboratory parameters (hematology, clinical chemistry, urinalysis), vital signs measurements, and physical examination findings

6.2.1 Calculation or derivation of safety variables

6.2.1.1 Laboratory data

All laboratory safety data, incorporating hematology, clinical chemistry, and urinalysis data will be listed, with deviations from the normal range explicitly noted on the listings.

Continuous laboratory data will be summarized using standard summary statistics. Both absolute values and change from pre-dose baseline will be summarized.

6.2.1.2 12-lead ECG data

Twelve-lead ECG data will be summarized and listed using standard summary statistics.

6.2.1.3 Vital signs

Vital signs data will be summarized and listed using standard summary statistics. Both absolute values and change from pre-dose baseline will be summarized. In addition, mean plots showing change within treatment group across time will be produced for absolute values.

6.2.1.4 Physical examination

Physical examination abnormalities will be listed.

6.3 Genetics as a co-variate

6.3.1 Calculation or derivation of genetic variables

A 9mL blood sample will be collected and genotyped to determine if subjects are PMs or EMs of CYP2C19.

Subjects coding for CYP2C19 *2/*2, *2/*3, or *3/*3 alleles will be considered PMs. Subjects coding for CYP2C19 *1/*1, *1/*2, or *1/*3 alleles will be considered EMs.

To control for other possible genetic factors that may contribute to increased exposure of rosuvastatin, all prospective subjects coding for OATP-C 1B1 *5 and *15, and/or BCRP 421C>A will be excluded from the study. Additionally, prospective subjects must code for wild-type CYP2C9 (*1 homozygous or heterozygous). There will be no other genetic research completed on the blood samples collected.

There will be no additional exploratory genetic research on the blood samples collected.

6.4 Statistical methods and determination of sample size

6.4.1 Statistical evaluation

A comprehensive SAP will be prepared and finalized before database lock.

6.4.2 Description of analysis sets

Statistical analyses for pharmacokinetic parameters will be performed on the evaluable population. An evaluable subject is defined as a subject satisfying the inclusion and exclusion criteria, completing all study procedures from the screening period to the final blood sampling for plasma levels of rosuvastatin, and had no major protocol deviation or violation.

All volunteers who received at least one dose of study medication will be included in the safety analysis

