Amended Clinical Pharmacology Study Protocol

Drug Substance Rosuvastatin Calcium
Study Code D3560C00059
Edition No. 1
Date

**A Phase I, Open Label, Parallel Group, Single and Multiple Dose Study
in Taiwanese Subjects Identified as CYP2C19 Poor Metabolizers or
Extensive Metabolizers Receiving 20 Milligrams of Rosuvastatin
Calcium**

Sponsor: AstraZeneca Taiwan, [name]

AstraZeneca Research and Development
Site Representative

The following Amendment(s) and Administrative Changes have been made to this protocol since the date of preparation:

Amendment No.	Date of Amendment
1	_____
Administrative Change No.	Date of Administrative Change
_____	_____
_____	_____

This submission /document contains trade secrets and confidential commercial information, disclosure of which is prohibited without providing advance notice to AstraZeneca and opportunity to object.

ASTRAZENECA PROCEDURES IN CASE OF EMERGENCY, OVERDOSE OR PREGNANCY

In the case of a medical emergency you may contact the Study Delivery Team Leader. If the Study Delivery Team Leader is not available, contact the Study Delivery Team Physician at the AstraZeneca Research and Development site shown below.

Role in the study	Name	Address and Telephone number
Study Delivery Team Leader		
Study Delivery Team Physician		
Product Physician		

For further clarifications regarding:

- Procedures in case of medical emergency see Section [8.2](#)
- Procedures in case of overdose see Section [8.3](#).
- Procedures in case of pregnancy see Section [8.4](#)

PROTOCOL SYNOPSIS

A Phase I, Open Label, Parallel Group, Single and Multiple Dose Study in Taiwanese Subjects Identified as CYP2C19 Poor Metabolizers or Extensive Metabolizers Receiving 20 Milligrams of Rosuvastatin Calcium

Investigator

Study center, type and number of subjects planned

This will be a single center study conducted in Taipei, Taiwan.

Approximately 25 healthy Taiwanese subjects that have been genotyped as poor metabolizers (PMs) of CYP2C19 and 25 healthy Taiwanese subjects that have been genotyped as extensive metabolizers (EMs) of CYP2C19 will be recruited to obtain at least 40 evaluable subjects (20 for each group).

An evaluable subject is defined as a subject satisfying the inclusion and exclusion criteria, completing all study procedures from the screening period to the final blood sampling for plasma levels of rosuvastatin, and had no major protocol deviation or violation.

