Subjects will be admitted to the clinical research center (CRC) on Day -1. Day -1 assessments will be completed and blood will be collected for a pre-treatment (baseline) lipid profile. After an overnight fast, subjects will receive a 20 mg rosuvastatin calcium tablet on Day 1. Blood samples will be collected to 72 hours post-dose to assess the pharmacokinetic profile. On the morning of Day 4, (after the 72 hour blood collection) the subjects will again be dosed with 20 mg of rosuvastatin. The subjects will then be discharged from the CRC with study drug and instructions to take one 20 mg tablet of rosuvastatin calcium each morning for the next 2 days (Days 5-6). On the mornings of Days 7, 8, and 9 the subjects will return to the CRC to have blood collected for trough levels of rosuvastatin prior to dosing. After blood collection and dosing on Day 9, the subjects will leave the CRC with study drug and instructions to take one 20 mg tablet of rosuvastatin calcium each morning for the next 7 days (Days 10-16). The subjects will return to the CRC in the afternoon of Day 16 for readmission to the CRC. On the morning of Day 17, subjects will receive the last dose of 20 mg rosuvastatin calcium and blood samples will be collected to 24 hours post dose to assess the pharmacokinetic profile at steady-state. On Day 18, final assessments, including a blood sample to assess post-treatment lipid profiles, will be completed and the subjects discharged from the study.

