3.3.5.3 Procedures for handling incorrect enrolled subjects

Subjects not meeting the inclusion/exclusion criteria for this study should, under no circumstances, be enrolled - there can be no exceptions to this rule. If subjects not meeting the study criteria are enrolled in error, incorrectly randomized, or if subjects subsequently fail to meet the criteria for the study post enrollment, they shall be discharged from the study after proper exit assessments (physical exam, safety labs, etc.). These subjects will be included in the safety portion of the clinical study report, but will not be considered evaluable subjects for the pharmacokinetic or pharmacodynamic aspects of the study.

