- AUC_{ss} - area under the plasma concentration time curve during any dosing interval at steady state; calculated using the linear trapezoidal rule
- DF - degree of fluctuation; calculated as $(C_{ss,max} - C_{ss,min})/C_{ss,av} * 100\%$
- AR - accumulation ratio; calculated as $AUC_{(0-24)}(\text{Day 17})/AUC_{(0-24)}(\text{Day 1})$

Maximum concentration (C_{max}) and area under the concentration curve from zero to infinity (AUC) of rosuvastatin will be the primary variables for this study to summarize exposure in each subject. If AUC data cannot be determined in all subjects completing the study, area under the curve of plasma concentration against time from zero to last quantifiable concentration ($AUC_{(0-t)}$) will replace AUC as the primary variable.

CL/F

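### One completer set for all PK variables drops a finished Day 1–4 profile from the single-dose comparison when a subject leaves or deviates only after the 72-hour sample

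*Protocol*

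**What the plan says.** Protocol Section 6.4.2 names a single set for all PK statistics: "Statistical analyses for pharmacokinetic parameters will be performed on the evaluable population". An evaluable subject must meet the entry criteria, must be one "completing all study procedures from the screening period to the final blood sampling for plasma levels of rosuvastatin", and must be one who "had no major protocol deviation or violation". The synopsis gives the same definition and plans about 25 recruits per genotype group so that at least 20 per group are evaluable. Section 3.1 puts entry at 20–25 per group.

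Section 6.1.1 and the synopsis state that Cmax and AUC from zero to infinity "of rosuvastatin will be the primary variables for this study to summarize exposure in each subject". Both are listed among the single-dose variables. The steady-state measures have their own names (Css,max, AUCss and so on) and are also headed primary. If AUC cannot be obtained in every subject who completes the study, AUC(0-t) takes its place.

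Of the Day 1 dose, Section 3.1 says: "Blood samples will be collected to 72 hours post-dose to assess the pharmacokinetic profile". The Day 4 dose follows that sample (Sections 3.1 and 3.4.2). The last rosuvastatin sample in Table 3 is tube 35, on Day 18, 24 hours after the Day 17 dose.

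Under Section 3.3.5.3, subjects enrolled in error, and also those who stop meeting the criteria after enrollment, "will not be considered evaluable subjects for the pharmacokinetic or pharmacodynamic aspects of the study".

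**The concern.** The data for the two headline variables are all in hand before the second dose. Fourteen further doses follow (Days 4 to 17), nine of them self-administered at home (Days 5–6 and 10–16). Nothing that happens then can change a subject's Day 1 Cmax or AUC, yet a withdrawal, a missed procedure, a major deviation or a lapse of eligibility in that period removes those values from the comparison of poor metabolizers (PMs) with extensive metabolizers (EMs).

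Two things are at stake. The first is precision: usable single-dose profiles are set aside. The second is selection: entry to the main comparison depends on events after the outcome was measured, while subjects are taking the drug under study. Section 3.3.5.1 lists safety reasons and severe non-compliance among the grounds for discontinuation. If leaving were related to exposure, the selection would act on the quantity being compared. Because the output in Section 6.4.3.3 is geometric mean ratios with 90% CIs, the estimate and its interval are what the study delivers.

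**Working it through.** **1. Timeline against the set definition.**

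| Item | Complete at | Required for evaluability |
|---|---|---|
| Single-dose Cmax, AUC, AUC(0-t), half-life | 72 h, morning of Day 4 | all procedures to Day 18 |
| Multiple-dose variables | 24 h after the Day 17 dose, Day 18 | all procedures to Day 18 |
| Accumulation ratio (Day 17 over Day 1) | Day 18, needs both profiles | all procedures to Day 18 |

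The rule fits the second and third rows, not the first. No other section brings a later leaver back: the AUC(0-t) fallback is itself confined to subjects who complete, and Section 3.3.5.3 adds an exclusion.

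**2. The plan's own numbers.** There is no power calculation to reproduce. Recruiting 25 to obtain 20 is consistent with a 20% loss, 20/(1 − 0.20) = 25. That rate is implied by the two figures and is not stated. The allowance also covers losses before 72 hours, which no change of analysis set can recover. So the rule can discard between 0 and 5 complete single-dose profiles per group within the plan's allowance.

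**3. Precision.** The half-width of the 90% CI for the log ratio is t(0.95, n1+n2−2) × s × √(1/n1 + 1/n2), with s = √ln(1+CV²). The protocol gives no CV, so 30–60% is assumed. When 20 per group is compared with 25, s cancels:

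[1.686 × √(2/20)] / [1.677 × √(2/25)] = 0.533/0.474 = 1.124, or about 12% wider.

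Intervals around a true ratio of 1:

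| Assumed CV | 20 per group | 22 per group | 25 per group |
|---|---|---|---|
| 30% | 0.855–1.169 | 0.862–1.161 | 0.870–1.149 |
| 40% | 0.814–1.228 | 0.823–1.216 | 0.833–1.201 |
| 50% | 0.777–1.286 | 0.787–1.271 | 0.799–1.251 |
| 60% | 0.744–1.344 | 0.755–1.325 | 0.769–1.301 |

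The 12% applies only if 25 per group enter and all five losses per group come after the 72-hour sample. If nobody is lost after 72 hours, the cost is zero.

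**4. Bias.** If loss is unrelated to exposure, or acts alike in both groups, the ratio is not biased. For the other extreme, 25 log-normal subjects per group were simulated and the highest-exposure PMs removed, with no EM lost. The remaining PM geometric mean is multiplied by the factor shown. The ratio columns apply that factor to an assumed true PM/EM ratio of 1.30.

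| PMs lost | Factor, CV 40% | Ratio | Factor, CV 50% | Ratio |
|---|---|---|---|---|
| 1 | 0.969 | 1.26 | 0.962 | 1.25 |
| 2 | 0.944 | 1.23 | 0.931 | 1.21 |
| 3 | 0.920 | 1.20 | 0.903 | 1.17 |
| 5 | 0.879 | 1.14 | 0.853 | 1.11 |

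A milder case (also assumed): 2 of 25 PMs leave and average 0.5 SD above their group's log mean. The mean of the remaining 23 falls by 2 × 0.5/23 = 0.043 SD. With s = 0.385 (CV 40%) or 0.472 (CV 50%), 1.30 becomes about 1.28 or 1.27.

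**The case against.** The strongest defence is that one common set has a purpose. The primary objective covers both single and multiple dosing, the multiple-dose variables are also headed primary, and the accumulation ratio needs both profiles from the same subject. A common set keeps all PK tables on the same people. This stands as a reason for a completion rule for the multiple-dose variables and the ratio. It does not explain why the single-dose variables need it.

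The study is exploratory, its sample size is not statistically based, and no margin or decision rule hangs on the 90% CI. The target of 20 per group is already counted after the completer rule, so the plan can still meet it. This stands, and it limits the severity.

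A reader might infer that the single-dose comparison will be biased. The documents do not support that. Nothing in them links early exit to Day 1 exposure. Section 3.2.2 describes the drug as well tolerated and the risk as low, and several of the listed reasons for leaving, such as voluntary exit or loss to follow-up, need have nothing to do with exposure. A reader might also take 12% as the expected loss of precision. It is a ceiling: the plan states no dropout rate, and Section 3.1 allows entry of as few as 20 per group.

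Excluding subjects enrolled in error is legitimate, for instance when an excluded transporter genotype would confound exposure. That part of Section 3.3.5.3 should stay.

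Finally, Section 6.4.1 promises a SAP before database lock. That lowers the urgency, but Section 6.4.2 states the set affirmatively, so a SAP using another would depart from the protocol. The study is open label and subject numbers show genotype (Section 3.4.3), which is a further reason to settle the set in advance.

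**Conclusion.** The point holds for the single-dose variables. Sections 6.4.2 and the synopsis remove a valid Day 1–4 profile because of events that come after it is complete. For the multiple-dose variables and the accumulation ratio the rule is reasonable.

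The loss of precision runs from nothing to about 12% in CI width on the log scale. The bias runs from none to the worst case of 1.21–1.23 (2 PMs lost) or 1.11–1.14 (5 PMs lost) in place of 1.30. Those bias figures rest on an assumed ratio, an assumed CV of 40–50% and the extreme supposition that exactly the highest-exposure PMs leave and no EM does. They show what the rule permits and do not forecast what will happen. No error rate or planned decision is affected. Severity: should-fix.

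**What to change.** In Section 6.4.2 and the synopsis, replace the single PK set with two:

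1. **Single-dose PK set:** correctly enrolled subjects who met the entry criteria at Day 1, have a Day 1–4 profile sufficient to derive the variable, and have no major deviation affecting that profile up to the 72-hour sample. For AUC to infinity, judge sufficiency on AUC(0-t), so that the fallback can still operate.
2. **Multiple-dose PK set:** correctly enrolled subjects with a sufficient Day 17–18 profile and no major deviation affecting it.

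Compute the accumulation ratio in subjects who belong to both sets. State the target of 20 per group for each set.

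Two other places must follow. Reword the AUC(0-t) fallback in Section 6.1.1 and the synopsis to refer to the single-dose set in place of subjects completing the study. Limit the PK exclusion in Section 3.3.5.3 to subjects enrolled in error, so that failing the criteria only after the 72-hour sample does not remove a valid single-dose profile.

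The cost is wording in these sections and matching text in the SAP, with no extra subjects or samples. The number of subjects may differ between single-dose and multiple-dose tables. The present common completer set can be kept as a sensitivity analysis, which also shows whether later losses moved the single-dose ratio.

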6.4.3 Methods of statistical analyses

Statistical summaries will be carried out by the biostatistical group at AstraZeneca, Wilmington, Delaware using the SAS system Version 8.

Where standard summary statistics are referenced below, this will include the mean, standard deviation, median, minimum and maximum for continuous variables, and counts and percentages for discrete variables.

6.4.3.1 Demographic and baseline data

All demographic and baseline data, including medications, will be listed and summarized using standard summary statistics. No hypothesis test comparing the subjects that are EMs and the subjects that are PMs will be made.

6.4.3.2 Adverse Events

Adverse events will be summarized by System Organ Class and Preferred Term, using Medical Dictionary for Drug Regulatory Activities (MedDRA). All adverse event data will be listed for all subjects. Separate listings of all serious adverse events, deaths or other significant adverse events will be presented.

6.4.3.3 Pharmacokinetic data

Pharmacokinetic data will be summarized for each group, using descriptive statistics. Geometric means (including 95% CIs) and CV, will be calculated and listed. In addition, the geometric mean ratios (PMs vs. EMs) of AUC, AUC_(0-t), and C_{max}, (for rosuvastatin, N-desmethyl rosuvastatin, and rosuvastatin lactone) and metabolite to parent ratios, and their 90% CIs will be calculated. Half-lives for the two groups will be summarized using least squares means and the comparison between PMs and EMs will be by least squares mean difference and 90% CI.

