2. STUDY OBJECTIVES

2.1 Primary objectives

The primary objectives of this study are to:

- Explore the exposure of rosuvastatin calcium in Taiwanese subjects who have been identified as CYP2C19 PMs to exposure in Taiwanese subjects who have been identified as CYP2C19 EMs by examining the pharmacokinetic profile of rosuvastatin and its metabolites after single and multiple dosing of 20 milligrams (mg) rosuvastatin calcium
- Measure the effect of rosuvastatin calcium on lipid parameters of Taiwanese subjects after 2 weeks of daily dosing of 20 mg rosuvastatin calcium

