6. PHARMACOKINETIC, PHARMACODYNAMIC, SAFETY, GENETIC AND STATISTICAL METHODOLOGY

6.1 Pharmacokinetic / pharmacodynamic evaluation

6.1.1 Calculation or derivation of pharmacokinetic variables

The Clinical Pharmacokinetics Group, AstraZeneca, Wilmington, Delaware will carry out the pharmacokinetic analyses.

The pharmacokinetic variables of rosuvastatin, N-desmethyl rosuvastatin, and rosuvastatin lactone defined below will be calculated by non-compartmental methods using WinNonlin Enterprise version 4.1, Pharsight Corp., Mountain View, CA. The actual sampling times will be used in the pharmacokinetic calculations. The following parameters will be derived:

The primary variables to be assessed for rosuvastatin after a single dose are:

- C_{\max} - the observed maximum plasma concentration following a single dose
- AUC - area under the plasma concentration time curve, calculated by $AUC_{(0-t)}$ and then extrapolated to infinity by the addition of $(C_{\text{last}} / \lambda_z)$
- $AUC_{(0-t)}$ - area under the plasma concentration time curve from time zero to the last quantifiable plasma concentration (C_{last}), calculated using the linear trapezoidal rule
- AUMC - area under the first moment curve; AUMC will be calculated by the linear trapezoidal rule
- t_{\max} - the time to reach the observed maximum plasma concentration following a single dose
- λ_z - terminal elimination rate constant, calculated by log-linear regression of the terminal portion of the concentration time profile where there are sufficient data (a minimum of 3 plasma concentration values in the terminal log-linear phase, spanning an interval of at least 2 half-lives)
- $t_{1/2, \lambda_z}$ - half-life associated with the terminal slope (λ_z) of a semi logarithmic plasma concentration-time curve. Calculated as $\ln(2)/\lambda_z$
- MRT - mean residence time; calculated as $AUMC/AUC$
- CL/F - apparent oral clearance, calculated as Dose/AUC (rosuvastatin only). If for an individual, AUC cannot be calculated CL/F will not be calculated.
- Vd/F - volume of distribution (apparent) during terminal (λ_z) phase; calculated as $\text{Dose}/AUC * \lambda_z$; (rosuvastatin only)

The primary variables to be assessed for rosuvastatin after multiple dosing are:

- $C_{ss,max}$ - maximum (peak) steady state drug concentration in plasma during steady state dosing interval
- $C_{ss,min}$ - minimum (trough) steady state drug concentration in plasma during steady state dosing interval

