- $C_{ss,av}$ - average drug concentration in plasma during a dosing interval at steady station on administering a fixed dose at equal dosing intervals; calculated as AUC_{ss}/τ
- $t_{ss,max}$ - the time to reach the observed maximum plasma concentration at steady-state
- $t_{ss,1/2}$ - the apparent terminal half-life at steady-state
- AUC_{ss} - area under the plasma concentration time curve during any dosing interval at steady state; calculated using the linear trapezoidal rule
- DF - degree of fluctuation; calculated as $(C_{ss,max} - C_{ss,min})/C_{ss,av} * 100\%$
- AR - accumulation ratio; calculated as $AUC_{(0-24)}(\text{Day 17})/AUC_{(0-24)}(\text{Day 1})$

The secondary variables to be assessed for rosuvastatin metabolites N-desmethyl rosuvastatin and rosuvastatin lactone after a single dose are:

- C_{max} - the observed maximum plasma concentration following a single dose
- AUC - area under the plasma concentration time curve, calculated by $AUC_{(0-t)}$ and then extrapolated to infinity by the addition of (C_{last} / λ_z)
- $AUC_{(0-t)}$ - area under the plasma concentration time curve from time zero to the last quantifiable plasma concentration (C_{last}), calculated using the linear trapezoidal rule
- t_{max} - the time to reach the observed maximum plasma concentration following a single dose
- λ_z - terminal elimination rate constant, calculated by log-linear regression of the terminal portion of the concentration time profile where there are sufficient data (a minimum of 3 plasma concentration values in the terminal log-linear phase, spanning an interval of at least 2 half-lives)
- $t_{1/2,\lambda_z}$ - half-life associated with the terminal slope (λ_z) of a semi logarithmic plasma concentration-time curve. Calculated as $\ln(2)/\lambda_z$

The secondary variables to be assessed for rosuvastatin metabolites N-desmethyl rosuvastatin and rosuvastatin lactone after multiple dosing are:

- $C_{ss,max}$ - maximum (peak) steady state drug concentration in plasma during steady state dosing interval
- $C_{ss,min}$ - minimum (trough) steady state drug concentration in plasma during steady state dosing interval
- $C_{ss,av}$ - average drug concentration in plasma during a dosing interval at steady station on administering a fixed dose at equal dosing intervals; calculated as AUC_{ss}/τ
- $t_{ss,max}$ - the time to reach the observed maximum plasma concentration at steady-state

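### The PM/EM geometric mean ratios name only single-dose AUC, AUC(0-t) and Cmax, so steady-state exposure (AUCss, Css,max) has no planned between-group estimate although the first primary objective covers multiple dosing

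*Protocol*

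**What the plan says.** Protocol Section 2.1 sets out to explore PM against EM exposure through the "pharmacokinetic profile of rosuvastatin and its metabolites after single and multiple dosing of 20 milligrams (mg) rosuvastatin calcium".

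Section 6.1.1 then defines two separate sets of rosuvastatin variables and calls both primary. In the single-dose set, Cmax is "the observed maximum plasma concentration following a single dose"; AUC (to infinity) and AUC(0-t) stand in the same set. The second set opens with "The primary variables to be assessed for rosuvastatin after multiple dosing are" and has eight members: Css,max, Css,min, Css,av, tss,max, tss,1/2, AUCss, DF and AR. AUCss has its own definition, the "area under the plasma concentration time curve during any dosing interval at steady state". The section closes by naming Cmax and AUC of rosuvastatin, with AUC(0-t) as fallback for AUC, as the variables that summarize exposure for the study.

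For the analysis, Section 6.4.3.3 gives all pharmacokinetic data descriptive statistics by group and geometric means with 95% CIs. It adds "the geometric mean ratios (PMs vs. EMs) of AUC, AUC_(0-t), and C_{max", for rosuvastatin, N-desmethyl rosuvastatin and rosuvastatin lactone, together with "metabolite to parent ratios, and their 90% CIs will be calculated". A last sentence, which begins "Half-lives for the two groups will be summarized using least squares means and the comparison between PMs and EMs", compares half-lives by least squares mean difference with a 90% CI. The synopsis carries the same list.

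**The concern.** The objective, the variable list and the analysis do not line up. The objective asks about exposure after multiple dosing and the variable list supplies steady-state exposure measures called primary, but the list of between-group ratios stops at the single dose. The protocol uses distinct symbols for the two situations, so AUC and Cmax in the ratio list cannot readily be read as including AUCss and Css,max.

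At stake is a direct answer, with its uncertainty, to the multiple-dose part of a primary question. Steady-state exposure is what a person on daily treatment experiences. The Day 17 profile that would supply it is already in the design: 13 of the 35 pharmacokinetic samples per subject in Table 3 (tubes 23 to 35). If ratios for AUCss and Css,max are added only at the reporting stage, they go beyond the list that the protocol fixed.

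**Working it through.** **Step 1: match the analysis to the variables.** The protocol states no figure to reproduce, so the first check sets the sections side by side.

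| Item in the between-group analysis (6.4.3.3, synopsis) | Where 6.1.1 defines it | Covers multiple dosing? |
|---|---|---|
| Ratio of Cmax | Single-dose lists; definition names the single dose | No |
| Ratio of AUC | Single-dose lists only | No |
| Ratio of AUC(0-t) | Single-dose lists only | No |
| Metabolite-to-parent ratios | No parameter or day named | Possibly |
| Half-life difference | Both t1/2,λz (single dose) and tss,1/2 (steady state, rosuvastatin only) | Can cover tss,1/2 |

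Of the eight rosuvastatin multiple-dose primary variables, none is named in the ratio list and one (tss,1/2) can fall under the half-life comparison. AUCss, Css,max, Css,min and Css,av have no planned PM/EM estimate. Half-life is not an exposure measure, so it does not fill the gap in the objective.

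**Step 2: how precise would the missing ratio be?** Inputs:
- n = 20 evaluable subjects per group (synopsis).
- Between-subject CV: not given in the protocol; assumed to lie between 30% and 60%.
- t(0.95, 38) = 1.686.

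With log-normal data and equal variances, the 90% CI is the ratio multiplied and divided by

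exp( t(0.95, 2n−2) × √ln(1+CV²) × √(2/n) ).

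For CV 40%: √ln(1.16) = 0.385, √(2/20) = 0.316, and exp(1.686 × 0.385 × 0.316) = 1.23.

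| Assumed CV | Factor, 20 per group | Factor, 25 per group |
|---|---|---|
| 30% | 1.17 | 1.15 |
| 40% | 1.23 | 1.20 |
| 50% | 1.29 | 1.25 |
| 60% | 1.34 | 1.30 |

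An observed ratio of 1 at CV 40% and 20 per group would have a 90% CI of 0.81 to 1.23.

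**Step 3: can a reader recover the ratio from the planned output?** Yes, with some work. At CV 40% and 20 per group, each group's geometric mean has a 95% CI factor of 1.198. Its log standard error is ln(1.198)/2.093 = 0.086. For two independent groups with equal standard errors, the standard error of the log ratio is 0.086 × √2 = 0.122, and exp(1.686 × 0.122) = 1.23, the value in Step 2. The information is not lost, but the estimate is not planned.

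**The case against.** The strongest defence is that the ratio list follows the protocol's own hierarchy. Section 6.1.1 and the synopsis name Cmax and AUC, with AUC(0-t) as fallback, as the variables that summarize exposure, and those three are exactly the ones that get ratios. The objective is to explore, the study is declared exploratory and not powered for a formal comparison (synopsis, Section 6.4.4), and Section 6.4.1 promises a comprehensive SAP before database lock, which could add rows to a table. This stands as a reason to keep the single-dose variables in the lead and to rate the point below a required correction. It does not remove the mismatch. Being exploratory sets aside testing and power, not estimation, and the protocol already plans estimation for the single dose. Nor did it leave the list open: it fixed named parameters twice, and the steady-state variables that it also calls primary are absent both times.

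Three stronger readings are tempting, and the documents do not support them.
- A reader might infer that the multiple-dose part gets no between-group estimate of any kind. The half-life comparison is not tied to Day 1 and can cover tss,1/2, and the metabolite-to-parent ratios name no day.
- A reader might infer that the two weeks of dosing are there for steady-state exposure and are therefore wasted. Section 3.2.1 justifies the two weeks by the lipid effect, which serves the other primary objective. The three trough samples on Days 7 to 9 serve, according to the synopsis, to show whether steady state is reached, and would not enter a ratio of AUCss or Css,max.
- A reader might infer that only a crude check of overlapping intervals would remain, with non-overlap at about 2.8 standard errors of the difference against 1.7 for a 90% CI of the ratio. That contrast mixes 95% and 90% levels. At a common 95% level with t quantiles it is about 2.96 (2.093 × √2) against 2.02. The protocol does not plan an overlap check, and Step 3 shows that the ratio can be derived.

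**Conclusion.** The point holds for the steady-state exposure variables. The first primary objective includes multiple dosing and the protocol calls AUCss and Css,max primary, yet the PM/EM ratios with 90% CIs name only single-dose parameters. A multiple-dose comparison could come only from half-life and possibly from the metabolite-to-parent ratios.

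The severity is moderate. The declared lead exposure variables do get ratios, no stated result would be wrong, and no data would be lost. The missing ratio would carry a 90% CI of about ×/÷ 1.17 to 1.34 with 20 per group. That range rests on the assumed CV of 30% to 60%, log-normal data with equal variances, and all 20 evaluable subjects in each group contributing a Day 17 profile. The textual finding rests on none of these assumptions. The SAP is not among the documents; if it already adds these ratios, only the protocol wording needs aligning.

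**What to change.** In Section 6.4.3.3 and the synopsis:
- Add AUCss and Css,max, for rosuvastatin, N-desmethyl rosuvastatin and rosuvastatin lactone, to the list of PM/EM geometric mean ratios with 90% CIs.
- State that the half-life and metabolite-to-parent comparisons are made for both Day 1 and Day 17, and name the parameters used for the metabolite-to-parent ratios. Section 6.1.1 lists a steady-state half-life for rosuvastatin only, so the Day 17 half-life comparison applies to the parent unless that list is extended.

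Single-dose AUC and Cmax can remain the lead variables. Ratios for Css,min or AR are optional; nothing in the protocol's hierarchy requires them.

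The cost is a sentence or two in each place and a few more table rows. No subjects, samples or visits are added, because Day 17 is already sampled to 24 hours. The change should be made before database lock, in step with the SAP.
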